8.5.2 Visit 2 (day 14 \pm 1 day)

Subjects will be requested to return to site for Visit 2, 13 to 15 days after the first vaccination.

The investigator or designee will assess local tolerability (of previous vaccination site) and ask about any new concomitant medications or AEs occurred since the last visit. The subject's diary will be collected and checked for completeness.

A blood sample will be collected and PBMCs will be prepared for T cell analysis.

The subjects will be asked to return to study site for Visit 3 on study day 28 (\pm 5 days).

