8.5.4 Visit 4 (day 42 \pm 5 days)

Subjects will be asked to return for Visit 4, 37 to 47 days after Visit 1.

The investigator or designee will assess local tolerability (of previous vaccination site) and ask about any new concomitant medications or AEs occurred since the last visit. The subject's diary will be collected and checked for completeness.

A blood sample will be collected and PBMCs will be prepared for T cell analysis.

The subjects are invited to return to study site for Visit 5 on study day 56 (\pm 5 day).

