8.9.1 Safety Stopping Rules

Stopping rules are established at subject level and entire study level.

Individual Subjects Stopping Rules

The following are specific criteria for discontinuing individual subjects from further vaccination, but not from completing scheduled follow-up assessments, unless the subject is explicitly withdrawn from the study:

- Subjects who develop serious adverse reaction (SAR) at the discretion of the investigator
- Subjects who develop a potentially life-threatening (grade 4) solicited systemic adverse reaction that occurs without alternative etiology within 7 days after the study vaccination
- Subjects who develop a medical condition for which continued participation, in the opinion of the investigator, would pose a risk to the subject or would be likely to confound interpretation of the results
- Subjects who become pregnant during the treatment phase of the study
- Subjects who experience anaphylaxis within 24 hours or generalised urticaria within 72 hours after administration of the study vaccine

If any of these occur, appropriate measures to treat the subject will be taken and the sponsor or the sponsor designee will be notified immediately.

Entire Study Stopping Rules

The study will be stopped (no new enrolments and no additional vaccine administered) pending a safety review by the investigator and the sponsor, if any of the following occurs:

- One or more subjects experience a serious adverse reaction (SAR), based on the current reference safety information (Investigator's Brochure)
- One or more subjects' deaths assessed by the investigator, safety manager or sponsor as related to investigational product
- One or more subjects develop laryngospasm, bronchospasm or anaphylaxis within 24 hours of vaccine administration
- Three or more subjects develop injection-site ulceration, abscess or necrosis
- Three or more subjects experience generalised urticaria within 72 hours after administration of study product

Upon completion of this review, the sponsor will determine if study enrolment or treatment should be discontinued, or if study enrolment and treatment may continue according to the protocol.

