11.7 Subject Diary

The subjects will be instructed to complete a diary for 7 days after each vaccination to document local and systemic tolerability as well as body temperature.

Solicited local and solicited systemic AEs will be assessed by the subjects themselves by checking for presence of the listed symptoms and measuring the size of the affected area where appropriate (a template will be provided for local reaction grading, as shown in Appendix 1). The diary will also provide space for recording unsolicited AEs and concomitant medication.

Recording should be done approximately at the same time each day, starting on the day of vaccination. The first entry should be made 6 hours ± 1 h after vaccination at Visit 1 and Visit 3.

The subjects' diaries will be collected and verified for completeness by the investigator at Visit 2 and Visit 4. Any AE recorded in the subject diaries will be entered in the eCRF by the investigator or authorised delegates. The investigator will re-evaluate the severity of the reported local and systemic AEs according to the below Tables 5 and 6.

Diary solicited systemic AEs include: nausea, vomiting, headache and fatigue, also to be documented in the eCRF.

In addition, body temperature will be recorded daily for 7 days and fever will be graded by the investigator according to the FDA Guidance for Industry. For details see below Table 6.

Table 5: Grading of Local Reactions

Local reaction to injectable product	Mild (grade 1)	Moderate (grade 2)	Severe (grade 3)	Potentially life threatening (grade 4)
Pain	Does not interfere with activity	Interfere with activity or repeated use of non-narcotic pain reliever	Prevents daily activity or repeated use of non-narcotic pain reliever	Emergency room (ER) visit or hospitalisation
Tenderness	Mild pain to touch	Pain with movement	Significant pain at rest	ER visit or hospitalisation
Erythema/ Redness¹	≤ 5 cm	5.1–10 cm	> 10 cm	Necrosis or exfoliate dermatitis
Swelling²	≤ 5 cm and does not interfere with activity	5.1–10 cm or interfere with activity	> 10 cm or prevents daily activity	Necrosis
Itching	Does not interfere with activity	Interferes with activity or repeated use of non-narcotic pain reliever	Prevents daily activity or repeated use of anti-inflammation and pain-relieving ointment	Emergency room (ER) visit or hospitalisation

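### The study-level stopping rules count reactions within 24 and 72 hours of injection, but after the 2-hour check no contact or diary review is scheduled until 13–15 days after dose 1 or 4–24 days after dose 2

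*Combined protocol and SAP*

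**What the plan says.** Protocol 8.9.1 gives the consequence of a study-level trigger: "The study will be stopped (no new enrolments and no additional vaccine administered) pending a safety review by the investigator and the sponsor". Three of the study-level triggers matter here:

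- "One or more subjects develop laryngospasm, bronchospasm or anaphylaxis within 24 hours of vaccine administration"
- "Three or more subjects experience generalised urticaria within 72 hours after administration of study product"
- "Three or more subjects develop injection-site ulceration, abscess or necrosis" (no time window)

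The remaining two, a serious adverse reaction and a related death, also have no window.

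Under 8.5.1 and 8.5.3 each subject is observed for two hours after injection, then goes home with a 7-day diary. For dose 1, 8.5.2 states: "Subjects will be requested to return to site for Visit 2, 13 to 15 days after the first vaccination". For dose 2, given at Visit 3, 8.5.4 states: "Subjects will be asked to return for Visit 4, 37 to 47 days after Visit 1". Section 10.2 has adverse events asked about at visits. Section 11.7 says the subjects' "diaries will be collected and verified for completeness by the investigator at Visit 2 and Visit 4". Neither protocol Table 2 nor the schedule in SAP 1.6 shows a call, remote diary review or visit in between.

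**The concern.** A rule that stops all vaccination is only as good as the count behind it. Two of these counts concern the first one to three days after injection, yet the scheduled data that feed them arrive at the next visit. A subject who has urticaria on day 2, recovers and notes it in the diary has followed the protocol, and the site need not learn of it until Visit 2 or Visit 4. If that subject is the third case, the threshold has been reached and injections continue.

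The risk falls on the other subjects. The setting makes a current count worth having: groups D and E (24 subjects) receive the highest nominal dose, group C (12 subjects) receives the new SPS formulation, and protocol 4.4.1 reports that adverse events and local reactions rose with dose in phase I.

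**Working it through.** **Inputs.** Visit 2 = day 14 ± 1, Visit 3 (dose 2) = day 28 ± 5 and Visit 4 = day 42 ± 5, all counted from Visit 1 (protocol 8.5.2–8.5.4, Table 2). Windows of 1 day and 3 days (8.9.1). 60 subjects, two injections each (9.3).

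**1. Reproduce the plan's windows.** 14 − 1 = 13 and 14 + 1 = 15; 28 − 5 = 23 and 28 + 5 = 33; 42 − 5 = 37 and 42 + 5 = 47. All agree with the visit text.

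**2. Injection to next scheduled contact.** After dose 1: 13–15 days. After dose 2, because both visits are anchored to Visit 1: minimum 37 − 33 = 4, nominal 42 − 28 = 14, maximum 47 − 23 = 24 days.

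**3. Lag from the close of each window to that contact** (interval from step 2 minus window length):

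| Window | After dose 1 | After dose 2 (nominal) |
|---|---|---|
| 24 h | 12–14 days | 3–23 days (13) |
| 72 h | 10–12 days | 1–21 days (11) |

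Injection-site lesions have no window, so the lag runs from onset to the next visit and is bounded by the intervals in step 2.

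**4. The affected subject's own second dose.** Visit 2 to Visit 3 is at least 23 − 15 = 8 and at most 33 − 13 = 20 days. Within the allowed windows, dose 2 therefore always follows Visit 2, and an event recorded there is known before that subject is injected again.

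**5. Other subjects injected meanwhile.** The documents give no accrual pace, so this is illustration only. First injections during the 10–12 days after the 72-hour window of a dose-1 case = weekly pace × 10/7 to weekly pace × 12/7:

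| Assumed pace | Weeks to enrol 60 | First injections in the lag |
|---|---|---|
| 5 per week | 12 | 7.1–8.6 |
| 10 per week | 6 | 14.3–17.1 |
| 15 per week | 4 | 21.4–25.7 |

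These figures assume no spontaneous report and enough subjects still to be enrolled when the third case occurs. Second injections falling due would be additional.

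**The case against.** The strongest reply is that the serious triggers do not depend on the schedule. Laryngospasm, bronchospasm and anaphylaxis would probably reach the site unprompted. Section 10.2 accepts verbal reports, 8.8 allows unscheduled visits, 8.9.1 requires immediate sponsor notification of individual cases of anaphylaxis or generalised urticaria and lets the study be suspended at any time, and 10.3 sets a 24-hour SAE clock. All of this stands and narrows the gap. But each safeguard starts only when the site or sponsor already knows, so none of them supplies the missing information about a non-serious event that the subject simply writes down. Urticaria is not among the systemic symptoms that 11.7 names for the diary and would depend on a free-text entry.

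Some stronger readings are tempting but unsupported:

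- A reader might infer that the 7-day criterion, "potentially life-threatening (grade 4) solicited systemic adverse reaction that occurs without alternative etiology within 7 days after the study vaccination", is starved of data too. It is listed only for individual subjects. It governs that subject's further vaccination, and after dose 1 Visit 2 comes in time (step 4). After dose 2 no vaccination remains to be withheld.
- A reader might infer that subjects are never told to call. The visit and diary sections contain no such instruction, but the diary form and consent pages are not available for review and may contain one.
- A reader might infer that groups D and E receive a dose above any used before. That is true only of nominal values. Protocol 4.5 gives earlier doses up to 5×10^5 ± 0.5 log, which reaches about 1.6×10^6. The new 1×10^6 ± 0.5 log starts at about 3.2×10^5, so the ranges overlap.

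**Conclusion.** The mismatch is real and narrow. The 24-hour and 72-hour study-level counts have no scheduled data source between the 2-hour check and the next visit. For the 72-hour count the scheduled lag is 10–12 days after dose 1 and 1–21 days (nominal 11) after dose 2; the 21-day figure needs Visit 3 and Visit 4 at opposite ends of their windows. The counts most exposed are non-serious generalised urticaria and injection-site ulceration, abscess or necrosis, where three cases must accumulate and none need lead to hospital.

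This rests on two assumptions: that the subject does not report the event unprompted, and that no contact is scheduled outside the documents reviewed. A reader might take the table in step 5 as an estimate of subjects exposed. It is not one. Without an accrual pace that number is unknown, and the mismatch does not depend on it.

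**What to change.** Reconcile protocol 8.9.1 with 8.5.1, 8.5.3, 11.7 and Table 2 (and SAP 1.6), so that the plan states how and when events feeding the study-level counts become known. All triggers, thresholds and clinical rules stay as they are.

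A low-cost way to do this is:

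- one brief scheduled telephone diary check by blinded site staff after each injection, once the 72-hour window has closed, with the study-level counts updated from it;
- a diary line asking subjects to report any event named in 8.9.1 promptly, if the diary or consent form does not already carry one. This matters most for injection-site lesions, which may appear after the call.

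The cost is 60 × 2 = 120 short calls, assuming existing staff can make them. Group E's placebo injection is included so that the calls do not differ by arm. No visit, blood sample or subject is added. The downside is staff time and slightly more complete adverse event capture, equally in all arms.

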Irrespective of the stopping rules the study may be temporarily suspended or prematurely terminated at any time if there is sufficient reasonable cause, and if agreed to by both the investigator and the sponsor as being in the best interests of subjects and justified on either medical or ethical grounds. In terminating the study, the sponsor, the CRO, and the investigator will ensure that adequate consideration is given to the protection of the subjects' interests.

Whenever the study is stopped the competent authorities and ethical committees will be informed.

In case the entire study has to be discontinued prematurely, all concerned subjects should be asked to perform an early termination visit.

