8.10 End of Study

The end of study will be defined as the date of the last visit of the last subject. The study will then be stopped. For premature termination or suspension of the study, refer to section 8.9.1

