10.1.3 Serious Adverse Event (SAE)

A serious adverse event is any untoward medical occurrence that:

- results in death
- is life-threatening
- requires inpatient hospitalisation or prolongation of existing hospitalisation
- results in persistent or significant disability/incapacity
- consists of a congenital anomaly or birth defect

Other 'important medical events' may also be considered serious if they jeopardise the participant or require an intervention to prevent one of the above consequences.

The term "life-threatening" in the definition of "serious" refers to an event in which the participant was at risk of death at the time of the event. It does not refer to an event which hypothetically might have caused death if it were more severe.

Any pregnancy occurring during the clinical trial and the outcome of the pregnancy will be recorded and followed up for congenital abnormality or birth defect, at which point it would fall within the definition of "serious".

NOTE: to avoid confusion or misunderstanding of the difference between the terms "serious" and "severe", the following note of clarification is provided: "Severe" is used to describe the intensity of a specific adverse event, while "seriousness" is used for defining regulatory reporting obligations as supplied above.

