10.1.6 Severity

AEs must be graded by a medically qualified person as being mild, moderate, severe or life-threatening and their approximate duration given. Definitions of severity are as follows:

Mild: an AE that requires minimal or no treatment and does not interfere with daily activities;

Moderate: an AE that is sufficiently discomforting to interfere with normal activities;

Severe: an AE that is incapacitating or prevents normal activities and may require systemic drug therapy or other treatment.

Potentially life threatening: an AE that requires immediate intervention to prevent death.

"life-threatening" refers to an AE in which the subject was at risk of death at the time of the event, it does not refer to an AE which hypothetically might have caused death if it were more severe.

Please see Appendix 1 for stencil to be used for grading local injection site reactions and Table 5 and 6 for grading of systemic and local reactions.

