Induration¹	≤ 1 cm Does not interfere with activity	> 1 to < 3 cm Interferes with activity or repeated use of non-narcotic pain reliever	≥ 3 cm Prevents daily activity or repeated use of anti-inflammation and pain-relieving ointment	Not applicable

¹ In addition to grading the measured local reaction at the greatest single diameter, the measurement should be recorded as a continuous variable.

² Swelling should be evaluated and graded using the functional scale as well as the actual measurement.

Table 6: Grading of Systemic Reactions

Systemic Reaction (General)	Mild (grade 1)	Moderate (grade 2)	Severe (grade 3)	Potentially life threatening (grade 4)
Nausea/ vomiting	No interference with activity or 1-2 episodes/ 24 hours	Some interference with activity or >2 episodes/ 24 hours	Prevents daily activity, requires outpatient IV hydration	Emergency room (ER) visit or hospitalisation for hypotensive shock
Diarrhoea	2-3 loose stools or < 400 gms/ 24hours	4-5 stools or < 400-800 gms/ 24hours	6 or more watery stools or >800 gms/ 24 hours or requires outpatient IV hydration	ER visit or hospitalisation
Headache	No interference with activity	Repeated use of non-narcotic pain reliever >24 hours or some interference with activity	Significant; any use of narcotic pain reliever or prevents daily activity	ER visit or hospitalisation
Fatigue	No interference with activity	Some interference with activity	Significant; prevents daily activity	ER visit or hospitalisation
Myalgia	No interference with activity	Some interference with activity	Significant; prevents daily activity	ER visit or hospitalisation
Illness or clinical AE (as defined according to applicable regulations)	No interference with activity	Some interference with activity not requiring medical intervention	Prevents daily activity and requires medical intervention	ER visit or hospitalisation
Fever (°C)	38.0 - 38.4	38.5 - 38.9	39.0 - 40.0	>40.0

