16.2 Study Termination

If the sponsor or the investigator decides to terminate the study before it is completed, they will notify each other in writing stating the reasons for early termination. In terminating the study, the sponsor and the investigator will ensure that adequate consideration is given to the protection of the subjects' interest. The investigator, sponsor or CRO will notify the relevant ethics committee and regulatory authority in writing in accordance with local requirements. Documentation will be submitted for filing in Central File and Investigator File.

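### Section 8.9.1 lets a grade 4 systemic reaction that is not an SAR stop only that subject, gives neither party alone the power to pause all dosing, and conflicts with 16.2 on who may terminate

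*Combined protocol and SAP*

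**What the plan says.** The study-level list in protocol 8.9.1 stops enrolment and vaccination, pending review by the investigator and the sponsor, for any of five events:

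- one SAR;
- one related death;
- one case of laryngospasm, bronchospasm or anaphylaxis within 24 hours;
- ulceration, abscess or necrosis at the injection site in three subjects;
- generalised urticaria within 72 hours in three subjects.

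After that review the sponsor decides whether to continue.

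Grade 4 systemic reactions appear only in the list for individual subjects: "Subjects who develop a potentially life-threatening (grade 4) solicited systemic adverse reaction that occurs without alternative etiology within 7 days after the study vaccination". For events on that list, "the sponsor or the sponsor designee will be notified immediately".

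A closing paragraph covers everything else. Whatever the triggers say, the study may be suspended or ended early for sufficient cause, "and if agreed to by both the investigator and the sponsor as being in the best interests of subjects". Section 8.10 sends the reader back to this text: "For premature termination or suspension of the study, refer to section 8.9.1". Section 16.2 is worded differently: "If the sponsor or the investigator decides to terminate the study before it is completed, they will notify each other in writing".

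**The concern.** The study-level list responds to non-serious allergic and injection-site events but not to non-serious systemic reactions, which the diary is designed to collect. For those, any study-wide pause depends on the closing paragraph of 8.9.1, which asks for both parties' agreement.

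This matters somewhat more here than in a repeat of known doses. Groups D and E (12 + 12 = 24 subjects) receive 1×10^6 TCID50, and the highest earlier dose in section 4.5 is 5×10^5, a nominal ratio of 2. The step is modest: the earlier ±0.5 log tolerance already reached 5×10^5 × 10^0.5 = 1.6×10^6. Section 4.4.1 does report that adverse events increased with dose in phase I.

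At stake is whether a reaction graded potentially life-threatening leads to a study-wide look before the next subject is dosed, and whether the site and the sponsor know who may call that pause.

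**Working it through.** The plan gives no operating characteristics for its stopping rules, so there is no figure to reproduce. The check is mainly textual, followed by a calculation of how often the proposed trigger would fire.

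**1. Can a reaction be grade 4 and not an SAR?**

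- The solicited systemic terms in 11.7 are nausea, vomiting, headache and fatigue. Body temperature is recorded as well and fever is graded. I count fever as solicited.
- Section 11.7 has the investigator grade these by Table 6. There, fever above 40.0 °C is grade 4, and so is an emergency room visit for headache or fatigue.
- Seriousness is defined in 10.1.3. Its hospital criterion is "requires inpatient hospitalisation or prolongation of existing hospitalisation". An emergency room visit without admission and a temperature reading are not listed.
- The general grade 4 definition in 10.1.6 is stricter than Table 6: "an AE that requires immediate intervention to prevent death". An event meeting it would almost always be serious.

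So the answer is yes, but only for fever above 40.0 °C or an emergency room visit without admission, judged neither life-threatening nor medically important. In that case the individual rule applies and no study-level rule does.

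**2. Who may act on an off-list event?**

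| Step | 8.9.1, closing paragraph | 16.2 |
|---|---|---|
| Temporary suspension | both parties agree | not addressed |
| Early termination | both parties agree | either party decides, then gives written notice |

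The conflict is over termination. On suspension only 8.9.1 speaks, and it names no single party.

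**3. How often would a study-level grade 4 trigger fire?**

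- Phase II interim severity counts (section 4.4.2): 468 mild + 145 moderate + 11 severe = 624, which is every reported event. If grade 4 was a separate category, there were none.
- Number on MV-CHIK: 69/0.324 = 213; controls 17/0.340 = 50; 213 + 50 = 263, the number treated.
- One-sided 95% upper bound for 0/213: 1 − 0.05^(1/213) = 0.0140, or 1.4% per subject.
- Chance of at least one in 60 subjects, 1 − (1 − p)^60:

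| p | Source | Chance of firing |
|---|---|---|
| 0.1% | assumed | 5.8% |
| 0.5% | assumed | 26.0% |
| 1.4% | upper bound | 57.0% |

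Other percentages in 4.4.2 imply a different split: 33/0.144 = 229 and 3/0.088 = 34, which also sum to 263. With 229 the bound is 1 − 0.05^(1/229) = 1.3% and the chance is 1 − 0.05^(60/229) = 54%, so the choice matters little.

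**The case against.** The case against is that the protocol already protects subjects well:

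- A single SAR, related death or anaphylaxis stops the study.
- Most grade 4 reactions would be SARs. The individual rule already excludes another cause, and 10.1.3 lets an event count as serious if intervention was needed to prevent a listed outcome.
- Sections 8.9 and 8.9.1 let the investigator withdraw any subject, or stop further vaccination where continuing would pose a risk. At a single site that is substantial power.
- Sections 14.2 and 16.1 allow action on immediate hazards before approval.
- The sponsor hears of a grade 4 reaction at once.
- The choice of triggers is a design decision, and nothing in the documents requires a systemic one.

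Most of this stands and limits the size of the point. What it does not supply is a study-level response to the remaining grade 4 cases, or a sentence saying that one party may pause all dosing.

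A reader might infer that the protocol makes the reversible step harder than the irreversible one, with two parties needed to suspend and one to terminate. The documents do not support that cleanly. The joint-agreement condition in 8.9.1 covers termination as well as suspension, and 16.2 is a notification clause that implies sole authority without expressly granting it. What they show is a conflict between two sections.

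A reader might also size the gap by earlier severe events, such as the severe headache and pyrexia in phase I or the 11 severe events in phase II. Those counts mainly reflect grade 3 events. The remedy below adds no grade 3 count, so those rates do not measure what it would change.

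**Conclusion.** The point holds as a narrow gap and a drafting conflict, and it is worth correcting because correction is cheap. It does not show that subjects are left unprotected.

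The relevant size is the firing probability of the added trigger: about 6% to 57% over assumed rates from 0.1% to the 1.4% bound. This rests on one common rate for all 60 subjects, on grade 4 having been a separate category in the phase II counts, and on preliminary data at doses up to 5×10^5. The bound is therefore not a firm ceiling for groups D and E. In the other direction, many of these events would stop the study anyway as SARs, so the number of additional pauses would be smaller than these figures suggest.

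**What to change.** Amend 8.9.1 in two places.

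1. Replace the joint-agreement clause with: *Either the investigator or the sponsor may suspend enrolment and vaccination immediately; the study-level safety review and restart decision then follow the same procedure as for a triggered stop.* Align the termination wording with 16.2. Using the existing restart procedure, in which the sponsor decides after the review, avoids two restart rules in one section.
2. Add to the study-level list: *One or more subjects meet the individual grade 4 solicited systemic criterion.*

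No grade 3 count is proposed. Clusters of grade 3 reactions can be handled under item 1.

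The cost is one protocol amendment, with no new role and no change in sample size. The downside is an occasional unneeded pause. A pause that outlasts the ±5-day window for Visit 3 puts some second doses out of window. SAP 2.9 lists substantial window violations at vaccination visits as major deviations, so in groups of 12 a long pause could remove subjects from the per-protocol population used for the primary analysis. A prompt review limits that risk.
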